5.2 Sample Collection/Labelling/Logging

Whole mouth saliva will be collected into a universal tube. All samples will be pseudo-anonymised and code break sheet will be located in CHMI offices in a secure password protected database in Microsoft Excel or Access on an encrypted PC.

5.3 Sample Analysis Procedures

See 5.1

5.4 Sample Storage Procedures (if applicable)

All samples will be stored in an HTA licensed -80°C freezer until ready for testing. DNA extracted from samples will be stored in an HTA licensed -80°C freezer until ready for sequencing. (Designated Individual [name], HTA License number 12521, Person Designate: [name])

5.5 Data Recording/Reporting

The data obtained during this study will comply with community standards for research data. King's College London aspires to ISO 27001 standards for data security. All hard copy data and link codes will be kept in a GSTT locked and secure filing cabinet in a locked room based in the PI's office Department of Periodontology, Faculty of Dentistry, Oral and Craniofacial Sciences in Guys Dental Hospital. Additional back up of link codes will be stored on secure GSTT storage. All pseudoanonymised electronic data will be held on KCL firewalled computers, subject to KCL standard audits. In addition, data will be stored at KCL high performance computers with weekly backup program. Data will be recorded by a dedicated technician who will be HTA trained.

Data analyses:

The immunological markers will be compared between the healthy controls, asymptomatic and symptomatic COVID-19 patients using Mean, Median and non-parametric tests like Anova and Mann-Whitney rank sum tests. The immunological markers in the blood and SWMF will be compared and analysed at various time points of the disease progression. The key immunological parameters will be compared with the oral microbiome data to identify key biomarkers that may be indicative of the pathogenesis of the disease. These parameters will also be compared between the South Asian and the British-Caucasian population recruited in the UK. At the conclusion of the study, all the above analyses of the immunological and oral microbiome parameters will be compared among the age-matched and disease-matched participants in the UK and a collaborative, parallel study performed by collaborators in Chennai, India.

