2.1. Trial Objectives

- Primary Objective

The key aim of this research in South Asian populations and White British populations, is to find out whether differences in COVID-19 morbidity and mortality in similar populations in the UK might be related to mucosal immunity expressed in the mouth and to the oral microbiome (the total bacteria, fungi and viruses living in the mouth). This will be achieved by determining

whether in the mouth there are differences between the participant groups of mucosal natural immunity (innate immunity), immune responses to SARS-COV2 antigens (adaptive immunity), or the oral microbiome

- Secondary Objectives

1. To determine whether differences in mucosal immunity or differences in the oral microbiome correlate with susceptibility to COVID-19 infection, or to progression and recovery from the disease.

2. To determine whether the presence of pre-existing oral disease is related to susceptibility to SARS-CoV2 infection, to severity of COVID-19 disease or relates to the nature of mucosal immunity and to the composition and activity of the oral microbiome

- Primary End Point

- Collection, processing and analysis of samples. Statistically significant quantitative differences in measured mucosal innate immune factors, mucosal adaptive immune factors and/or in the oral microbiome in relation to 1) a comparison between South Asian and White British populations in the UK 2) the degree of severity of COVID in South Asian and White British participants in the UK

- Secondary End point

- Generation of raw data.
- *a comparison between South Asian populations in the UK and in Chennai, India.

**Note: This is the UK part of an international research collaboration between the UK (funded by the MRC) and India (funded by the DBT) with research being carried out separately but in parallel in the two Countries and generating results which will be directly compared.*

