2.4 Trial Statistics

Statistical advice indicates that with expected variation in both immunological and microbiome parameters, between 30 and 50 values per parameter would be optimal to demonstrate statistical differences on a cross sectional basis (more than 21 for immunological samples, more than 30 for microbiome samples) and that 30-40 per parameter would be optimal on a sequential basis. We

have therefore aimed for a minimum of 50 and a maximum of 100 participants for the cross sectional comparison, and between 30 and 50 participants on a longitudinal basis. Groups of 100 for the cross-sectional part of the study and 50 for the sequential also allow for the unexpected withdrawal of participants and leave sufficient numbers of samples for statistical analysis.

The microbiome, clinical data and immunome data will be associated using Spearman correlations. A Mann–Whitney U-test will be used to determine the median differences of continuous clinical variables. For more than two groups, the Kruskal–Wallis test with post-hoc Dunn test will be used. The association between the prototype prevalence, immunome and clinical data will be modelled with single (univariate) or multiple (multivariate) dependent variables (clinical & immunome metadata features) and will be performed using multinomial or binomial logistic regression.

Standard pipelines and statistical methods already in use within the group will be used for oral metagenome data. The data will be initially quality controlled and trimmed. Human contaminant sequences will be removed from reads by mapping against a human reference genome using Bowtie2. Scaffolds will be assembled from filtered reads using SPAdes. SAMtools will be applied to generate statistics for each filtered scaffold. The scaffolds will be merged to one scaffold file and bacterial genes from the file will be identified using Prodigal. The genes will be clustered and redundant genes will be removed using CD-HIT. Next all the unmapped reads will be mapped to the list of assembled genes and using METEOR software suite the gene counts will be generated for each sample and according to the depth of the sample sequence data, the count table will be downsized. Then the updated count table will be normalized to the gene length and converted to a frequency matrix, which we call the Gene Abundance Matrix.

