3.1 Inclusion Criteria

Inclusion criteria
	
 • South Asian and White British persons and those diagnosed with symptomatic or asymptomatic COVID-19 infection, or recovered from COVID infection or previously uninfected. • Aged 18 or over. Able to understand and consent. • For inpatient groups: Confirmed COVID-19 positivity, symptoms and symptom onset within the past 21 days; Be recently (within 7 days) hospitalised with COVID-19 disease; Have COVID-19 disease proven by PCR testing for SARS-CoV-2 within the last 21 days; • Uninfected subjects: no history of COVID-19; not vaccinated; (negative for anti-SARS-CoV2 nucleoprotein antibodies at lab)
---------------------------	--

	
 • Recovered groups: Have had COVID-19 disease proven by PCR testing for SARS-CoV-2. • Those willing to participate on a single occasion but unwilling to participate with longitudinal samples will not be excluded. • Smoking, obesity, diabetes, heart disease, antibiotics or treatment related to COVID is not excluded.
--	--

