4.3 Randomisation Procedures

Samples will not be randomized.

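### The primary contrasts by ethnicity and COVID severity rest on unadjusted tests in non-randomised groups, with no adjustment set named for either

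*Protocol*

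**What the plan says.** - **Endpoint (Protocol 2.1).** The primary endpoint includes "Statistically significant quantitative differences in measured mucosal innate immune factors, mucosal adaptive immune factors and/or in the oral microbiome". The protocol applies this to two contrasts, one by ethnicity and one by COVID severity.
- **Immune markers (5.5).** Controls, asymptomatic patients and symptomatic patients are compared "using Mean, Median and non-parametric tests like Anova and Mann-Whitney rank sum tests". The ethnicity sentence comes shortly after, "These parameters will also be compared between the South Asian and the British-Caucasian population recruited in the UK", and names no method of its own.
- **Other tests (2.4).** Mann-Whitney is named for continuous clinical variables, and "For more than two groups, the Kruskal–Wallis test with post-hoc Dunn test will be used". Gene richness and species abundance are compared between cohorts by a Wilcoxon test with Benjamini-Hochberg correction. Section 2.2 uses the term cohort for the South Asian and White British populations.
- **Regression (2.4).** Logistic models relate prototype prevalence, immunome and clinical data. Neither ethnicity nor an adjustment set is named, and the models are not linked to the primary endpoint.
- **Matching (5.5).** The only mention is that results "will be compared among the age-matched and disease-matched participants in the UK and a collaborative, parallel study performed by collaborators in Chennai, India".
- **Eligibility (3.1).** "Smoking, obesity, diabetes, heart disease, antibiotics or treatment related to COVID is not excluded".
- **Recruitment (Section 3 and its table).** Uninfected people come from advertising, non-COVID patients, A&E, testing and vaccination centres and PIC sites. Asymptomatic/mild cases come mainly from testing, with some from the wards and A&E. Moderate/severe cases are hospital patients. Recovered participants come from follow-up clinics, discharge letters, GP sites and advertising.

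**The concern.** These are observational groups. A Mann-Whitney, Wilcoxon, Kruskal-Wallis or one-way ANOVA test asks whether the groups differ as sampled. It cannot separate disease severity from the age, comorbidity or medication of the people each route supplies. Benjamini-Hochberg correction handles the number of tests and leaves confounding untouched.

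The protocol's own background links periodontal bacteria to diabetes and cardiovascular disease, and 3.2 measures glucose in order to screen for diabetes. No named comparison uses either fact. Vaccination raises the same issue, because antibodies to spike peptides are an outcome (5.1). Section 3 admits vaccinated uninfected people while 3.1 lists that group as not vaccinated; those two passages must be reconciled.

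The aim in 2.1 is explanatory: whether outcome differences might be related to mucosal immunity and the microbiome. If a primary difference reaches significance, the named analyses could not say whether it belongs to severity or ethnicity, or to who was recruited.

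**Working it through.** **1. The plan's own figure.** Section 2.4 asks for 30-50 values per parameter (more than 21 for immunology, more than 30 for microbiome) and targets 50-100 per group. It gives no alpha, power, SD or effect size, so the figure cannot be reproduced. Assuming two-sided 5%, 80% power and Mann-Whitney efficiency 0.955, the detectable difference is d = (1.960 + 0.842) × √(2/n) / √0.955:

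| n per group | 21 | 30 | 50 | 100 |
|---|---|---|---|---|
| d (SD) | 0.89 | 0.74 | 0.57 | 0.41 |

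The shifts examined below are well under these values, yet they still inflate the error rate.

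**2. Rejection rate with no true effect.** Let confounding shift one group by b SD. Then P(reject) = Φ(b/√(2/n) − 1.96) + Φ(−b/√(2/n) − 1.96).

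| b | n = 50 | n = 100 |
|---|---|---|
| 0.1 | b/0.200 = 0.50, giving 7.9% | b/0.141 = 0.71, giving 10.9% |
| 0.2 | 1.00, giving 17.0% | 1.41, giving 29.3% |

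Simulating the Mann-Whitney test itself (4,000 runs) for b = 0.2 gives 17.0% and 27.7%. The second is slightly below the formula because the rank test is a little less efficient than a comparison of means.

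**3. What would produce such a shift.** The protocol gives no confounder sizes, so all of these are assumptions.
- Age gap 10 years, SD 15, age-marker correlation 0.3: (10/15) × 0.3 = 0.20 SD.
- Mild: 5 years at 0.01 SD per year plus diabetes 10% v 20% with effect 0.3 SD: 0.05 + 0.03 = 0.08 SD. Simulated rejection is 7% (n=50) and 8% (n=100).
- Moderate: 10 years at 0.02 SD per year plus diabetes 10% v 25% with effect 0.5 SD: 0.20 + 0.075 = 0.275 SD. Simulated rejection is 23% and 43%.

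A rank-based linear model adjusted for the confounders rejected 3.8% to 6.1% of the time in every scenario run (2,000 runs each, Monte Carlo error about 0.5 points). That is a best case, since the model contained exactly the variables that caused the bias.

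**4. Severity mix, if ethnic groups were pooled.** Take a mirror-image fill at the limits of 50-100: South Asian 100/75/50/75 and White British 50/75/100/75 (uninfected, mild, severe, recovered), with assumed group effects 0/0.5/1/0.5 SD. The means are (37.5 + 50 + 37.5)/300 = 0.417 and (37.5 + 100 + 37.5)/300 = 0.583. The difference of 0.167 SD comes from the mix alone, and simulation rejects 47% of the time. This is a deliberately extreme fill. With Table 1's planned 100 in every cell the difference is zero.

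**The case against.** A SAP may exist, and covariate sets are often left to it. The sentence on ethnicity fixes no test for immune markers. What answers this is that the protocol does name tests for its primary comparisons, including the Wilcoxon test between population cohorts for the microbiome, and none takes a covariate. The choice is made, and it is a weak one.

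For a purely descriptive question, a marginal difference between groups is real and needs no adjustment. That is fair, and it is why the rank tests can stay as description. It does not meet the explanatory aim in 2.1.

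Several stronger readings are tempting but unsupported:
- **Batch.** A reader might take "Samples will not be randomized" as a rule about assay batches. It is the whole entry under a standard randomisation heading in a study without treatment. Section 2.2 mentions batch analysis only when discussing timing. Nothing says batches line up with groups.
- **Regression.** It might seem confined to microbiome clusters. Section 2.4 also brings in immunome and clinical data.
- **Recruitment.** The routes might be thought to differ by ethnicity. Within each subgroup they are shared; the difference in routes bears on severity.
- **Pooling and interaction.** No pooled ethnicity test is stated, and the hypothesis is not framed as an ethnicity-by-severity interaction.

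**Conclusion.** The point holds in this form. The primary contrasts are to be judged by statistical significance, the named comparisons carry no covariates, and neither contrast has a stated adjustment set. The severity contrast is the more exposed, because recruitment route differs between its groups by design. The ethnicity contrast is exposed through differing patient characteristics and, only if subgroups are pooled with unequal fill, through severity mix. Restrictions in 3.2 (malignancy, pregnancy, long-term immune suppression, immune-altering research) remove some sources of bias but none of those listed in 3.1.

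The size cannot be derived from the protocol. About 8-11% false positives per test at 0.1 SD and 17-28% at 0.2 SD (n = 50 to 100 per group) are illustrations resting wholly on assumed shifts; mild imbalance would do little harm. For any fixed shift, a larger sample raises the error rate.

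**What to change.** For each primary contrast, make the main analysis a covariate-adjusted regression per marker (linear on the log scale, rank-based or cumulative-logit):
- Include ethnicity and the four-level disease group as terms, so that ethnicity is compared within disease group.
- Adjust for age, sex, smoking and diabetes or glucose, and for vaccination status once the CRF records it.
- Use the same covariates for species abundance, keeping the Benjamini-Hochberg correction.
- Report with and without variables that may lie on the causal path: antibiotics, COVID treatment and periodontal status, and diabetes for the ethnicity contrast.
- Keep the rank tests as descriptive.

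An ethnicity-by-group term may be added as a secondary analysis. Spreading groups across assay batches is a sensible precaution; it does not correct a stated error.

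The cost is analysis wording, a few degrees of freedom, the need for complete covariate data and one CRF field. Age, sex, smoking, medication and medical history are already on the CRF (Section 10), and glucose is measured under 3.2.

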Number of Subjects/Patients	Up to 800 subjects will be recruited, comprising up to 400 SA and 400 WB, each including patients, recovered and uninfected subjects.
Trial Design	Cross sectional with longitudinal component. Samples of SWMF, and blood and a detailed mouth examination on all participants. Lymphocyte phenotypes in blood and SWMF compared, cytokines and serum and secretory antibodies to SARS-CoV2 antigens. DNA extraction from SWMF for meta-analysis of oral microbiome, and metabolome and proteome analysis
Endpoints	
 1. Patients recruited 2. Samples collected and processed 3. Generation of raw data
Main Inclusion Criteria	
 • South Asian* and White British persons and those diagnosed with current or past symptomatic or asymptomatic SARS-CoV2 infection, or uninfected. • Aged 18 or over. • Able to understand and consent. • For in patient groups: Confirmed COVID-19 positivity, symptoms and symptom onset within the past 21 days;
Statistical Methodology and Analysis	
A total sample size of up to 800 participants, up to 400 of which will provide samples at three further time points. Between 30 and 50 values per parameter would be needed to demonstrate statistical differences on a cross sectional basis and 30-40 per parameter on a sequential basis.
 
The microbiome, clinical data and immunome data will be associated using Spearman correlations. A Mann–Whitney U-test will be used to determine the median differences of continuous clinical variables. For more than two groups, the Kruskal–Wallis test with post-hoc Dunn test will be used.

*South Asian defined as those of Indian sub-continent origin.

There is no device or product used in this study

Glossary of Terms and Abbreviations

AE Adverse Event

AR	Adverse Reaction
ASR	Annual Safety Report
CA	Competent Authority
CI	Chief Investigator
CRF	Case Report Form
CRO	Contract Research Organisation
DMC	Data Monitoring Committee
EC	European Commission
GAfREC	Governance Arrangements for NHS Research Ethics Committees
GSTT	Guys & St Thomas Hospital
ICF	Informed Consent Form
ISRCTN	International Standard Randomised Controlled Trial Number
KCH	King's College Hospital
KCL	King's College London
MA	Marketing Authorisation
MS	Member State
Main REC	Main Research Ethics Committee
NHS R&D	National Health Service Research & Development
PI	Principal Investigator
QA	Quality Assurance
QC	Quality Control

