Notably, recent studies support the hypothesis that the oral microbiota is of relevance in both acute and chronic lung disease, with poor oral health associated with an increased risk of respiratory disease (Mammen et al 1999). A question is, therefore, whether inflammation in the oral cavity may predispose to SARS-CoV2 infection (Sampson et al 2020). We know that improving oral health results in a reduction in respiratory infections in ICU and nursing home patients (Azarpazhooh et al 2006). Of particular relevance to the current COVID-19 pandemic, risk factors including coughing, hyperventilation and mechanical ventilation have been shown to provide a pathway for members of the oral microbiota to penetrate the lower respiratory tract and cause disease (Bao et al 2020). Co-infections have been significant causes of mortality in many previous viral pneumonia pandemics, including the recent 2009 swine flu outbreak (MacIntyre, et al 2018), and these phenomena appear to be repeating for the current COVID-19 pandemic. Early metatranscriptome analyses indicate the presence of elevated levels of oral commensal bacteria in the bronchoalveolar lavage of COVID-19 patients (Shen et al 2020).

There is increasing evidence of disparities in susceptibility to SARS-CoV-2 infection and subsequent morbidity and mortality amongst groups of different ethnic origin. In the UK, South Asian populations have been identified as a particularly susceptible group, with a high percentage mortality in contrast to similar populations in India, even after taking into account the effect of socio-economic level and of co-morbidities. The extent to which social, environmental and biological factors differ in the two populations and contribute to differences in outcomes from COVID-19 is not known.

Our research will compare the oral microbiome, salivary innate and specific mucosal antibody responses and oral disease among SARS-CoV2-positive patients and controls in the UK and determine their diagnostic and prognostic utility. We will compare mucosal and systemic immunity in order to reveal biomarkers for risk of disease progression so as to enable early initiation of treatment.

The study is part of a UK-India partnership and at the end of the research, data from the UK will be compared with that derived from a similar study with our collaborators in India.

References

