2.2 Trial Design & Flowchart

Proposed Methodology: In this combined cross sectional and prospective longitudinal study, non-COVID infected subjects and SARS-CoV2-positive patients of South Asian origin or White British origin diagnosed to have, or who have had, asymptomatic, mild, moderate or severe disease as per WHO or the equivalent NIH criteria will be recruited. Peripheral blood (approx 17 ml divided into 5ml clotted, 2ml EDTA, 2ml fluoride, 8ml heparinised) and stimulated whole mouth fluid (SWMF) samples (approx 4ml) will be collected from all patients and from subgroups at three further time points at approximately 2, 4 and 12 weeks. (SWMF is a combination of saliva, gingival crevicular fluid, desquamated epithelial cells, some nasopharyngeal secretions, some serum transudate). In addition to medical data available for each patient, short questionnaires on oral health and diet, a clinical examination for oral health using “PSR akaBPE” – periodontal screening and recording/basic periodontal examination of periodontal health will be undertaken. The maximum periodontal pocket depth in mm on all standing teeth using a graduated periodontal probe and the presence of bleeding on probing will be recorded for each tooth. Missing teeth will be noted.

Further information on ethnicity of South Asians will be sought, eg from Pakistan, Bangladesh, North India, South India or Sri Lankan [Sinhalese, Tamil or Muslim].

Sequence of consent, examination and samples:

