6.5 Ethics Reporting

Reports of related and unexpected SAEs will be submitted to the Main REC within 15 days of the chief investigator becoming aware of the event, using the NRES template. The form will be completed in typescript and signed by the chief investigator. The Coordinator of the main REC will acknowledge receipt of safety reports within 30 days. A copy of the SAE notification and acknowledgement receipt should be sent to the R&D Directorate at GSTT.

8. Ethics & Regulatory Approvals

This protocol and related documents have been reviewed and approved by the OXFORD Research Ethics Committee (REC). The Chief Investigator will submit a final report at conclusion of the study within the timelines defined in the Regulations

9. Data Handling

[name] will act as custodian for the study data. The following guidelines will be strictly adhered to:

- Patient data will be pseudo-anonymised (unique code + initials).
- All data will be stored on a password protected computer.
- The study will be run to EU General Data Protection Regulations, 2018 and the UK Data Protection Act, 2018

10. Data Management

The data obtained during this study will comply with community standards for research data. King's College London aspires to ISO 27001 standards for data security. However, all pseudonymised electronic data will be held on KCL firewalled computers, subject to KCL standard audits. All hard copy data and link codes will be kept in a locked and secure filing cabinet in a locked room based in the PI's office ([name]). Department of Periodontology, Faculty of Dentistry, Oral and Craniofacial Sciences in Guys Dental Hospital. Additional back up of link codes will be stored on secure GSTT storage. In addition, study data will be stored at KCL high performance computers with weekly backup program. The Principal Investigator will maintain study documentation containing clinical data for all participants entered into the study in a secured, locked and alarmed room, ensuring the confidentiality of the information collected. Securing records includes placing written forms in locked file cabinets and/or sealed and labelled storage boxes in a locked room and alarmed room. Access will be denied to all persons with the exception of the Principal Investigator and his designees.

Case Report Form

The CRF will record all information below-

Basic clinical parameters and safety recording

Patient demographics including ethnicity

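### The UK–Chennai comparison is matched on age and disease but not on regional origin, so a difference on this secondary end point could partly reflect origin and not country

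*Protocol*

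**What the plan says.** Section 2.1 lists as a secondary end point "a comparison between South Asian populations in the UK and in Chennai, India". Its note describes two studies run in parallel, "generating results which will be directly compared".

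Section 5.5 (Data analyses) names how participants are made comparable across the two countries: results are to be "compared among the age-matched and disease-matched participants in the UK and a collaborative, parallel study performed by collaborators in Chennai, India". It names no other matching factor.

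The footnote to the Study Synopsis sets the scope of the UK group: "South Asian defined as those of Indian sub-continent origin". Section 2.2 shows how wide that is: "Further information on ethnicity of South Asians will be sought, eg from Pakistan, Bangladesh, North India, South India or Sri Lankan", with the Sri Lankan category divided further. The Case Report Form list under Section 10 has "Patient demographics including ethnicity", but the patient metadata list that follows it has no field for regional origin.

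The Introduction supplies the reason for looking at India. South Asians in the UK are described as a susceptible group, "with a high percentage mortality in contrast to similar populations in India", and the contribution of social, environmental and biological factors to the different outcomes is called unknown.

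**The concern.** The Introduction's argument rests on the two populations being similar apart from where they live. A UK–Chennai contrast speaks to that only so far as the two groups share the same regional origin. As planned, the UK side may mix participants of Pakistani, Bangladeshi, North Indian, South Indian and Sri Lankan origin, and the other side is a single South Indian city. Country and regional origin would then change together.

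Diet, oral habits and ancestry can vary by region and can plausibly affect the oral microbiome or mucosal immune markers. A UK–Chennai difference could therefore be read as an effect of living in the UK when part of it is a difference in origin. Larger samples would not help: they leave the bias as it is and make it more often significant. The protocol already seeks the variable that would show this, but does not use it.

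**Working it through.** The protocol gives no figure for this comparison, so there is nothing to reproduce. The calculation below shows the mechanism and its range; it is not an estimate of the actual bias.

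**Inputs from the protocol**
- UK South Asian sample: "comprising up to 400 SA and 400 WB" in all (Study Synopsis), in four sub-groups of up to 100.
- Group size for the cross-sectional comparison: minimum 50, maximum 100 (Section 2.4).

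**Assumptions, not in the protocol**
- The Chennai cohort is entirely South Indian and as large as the UK group.
- p, the share of the UK group of South Indian or Sri Lankan Tamil origin: 10–50%.
- d, the difference in a marker between that origin and the other origins: 0.1, 0.3 or 0.5 SD.
- No true country effect; two-sided 5% level; within-origin SD of 1; normal approximation for two means.

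**Formulas**
- Spurious country difference: b = (1 − p) × d.
- Standard error: se = √[(1 + p(1 − p)d²)/n + 1/n].
- Probability of rejection: Φ(b/se − 1.96) + Φ(−b/se − 1.96).

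**Worked case**, p = 0.10, d = 0.5, n = 100: b = 0.90 × 0.5 = 0.45; se = √[(1.0225 + 1)/100] = 0.142; b/se = 3.16; Φ(3.16 − 1.96) ≈ 0.89, and the second term is negligible.

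| d (SD) | p | b (SD) | Rejection, 50 v 50 | Rejection, 100 v 100 |
|---|---|---|---|---|
| 0.1 | 10% | 0.09 | 7% | 10% |
| 0.1 | 50% | 0.05 | 6% | 6% |
| 0.3 | 10% | 0.27 | 27% | 48% |
| 0.3 | 50% | 0.15 | 12% | 18% |
| 0.5 | 10% | 0.45 | 61% | 89% |
| 0.5 | 50% | 0.25 | 23% | 41% |

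These are probabilities for one marker that carries the stated regional difference, not the share of all markers that would be declared significant. With p = 100%, b is 0 and rejection returns to 5%.

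**Cost of restricting the UK side to the matching origin.** With p of 10–50%, between 10 and 50 remain of a sub-group of 100, and between 5 and 25 of a sub-group of 50. The detectable difference at 80% power against 100 Chennai participants is 2.80 × √(1/m + 1/100):
- m = 10: 0.93 SD
- m = 50: 0.49 SD
- m = 100 (no restriction): 0.40 SD

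**The case against.** A reader might infer that regional origin is established as a confounder and that the study would answer its India question wrongly. The documents do not support that.

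- The protocol does not give the Chennai study's eligibility, ethnic mix or sample size. That its participants are mainly South Indian is an inference from the site. Any South Indian or Tamil participants in the UK group make the confounding partial.
- The primary and secondary objectives do not mention India. The comparison is a secondary end point, worded as a comparison, with no stated aim of isolating a country effect. The Introduction gives a motive, not a causal contrast.
- The sizes rest on assumed values of p and d. At d = 0.1 SD the rejection rate barely leaves 5%. Section 2.4 also plans Benjamini-Hochberg correction for gene richness and species abundance, so the nominal 5% level does not carry over to those analyses. Section 2.2 has only the first 50 per group analysed for the microbiome, so the 100 v 100 column fits the immunological markers better.
- Making the origin-matched subset the main analysis would mostly take UK sub-groups below the protocol's own aim of 50 per group.
- Matching on origin would not remove every other difference between the countries.

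All of this stands, and it limits the claim. It does not remove it. It may also be said that covariates for a secondary comparison belong in the statistical analysis plan. Here, however, the protocol itself states the matching set and leaves out a variable that it says it will seek. A later analysis plan also cannot recover origin for participants in whom it was not recorded.

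**Conclusion.** The point holds in a limited form. As written, the UK–Chennai comparison sets a group drawn from the whole sub-continent against a Chennai cohort, with age and disease as the only named matching factors. If that cohort is mainly South Indian, part of any difference could be due to regional origin. The effect could be negligible (0.05–0.09 SD, with 6–10% rejection per affected marker at a nominal 5%) or substantial (0.15–0.45 SD, with about 12–61% at 50 v 50 and 18–89% at 100 v 100). Which applies depends on p and d, and the protocol gives neither.

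Only this secondary end point is touched; the comparison of South Asian and White British participants within the UK is not. A change is worth making because the variable is already sought and using it costs little.

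**What to change.** In Section 5.5, add that the UK–Chennai comparison will be stratified by recorded regional origin as well as matched on age and disease. Report UK participants of South Indian or Sri Lankan Tamil origin versus Chennai alongside the all-South-Asian versus Chennai contrast. Report the regional make-up of both cohorts, and state that the all-South-Asian contrast will not be attributed to country alone. Make the Section 2.2 origin categories a Case Report Form field completed for every South Asian participant.

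The cost is a few sentences and one field, plus agreement with the Chennai collaborators to supply the same information on their cohort. The statistical price is a small origin-matched stratum with a wide interval, which is why it should stand beside the overall comparison and not replace it. Adjusting for origin in a model would not avoid this: if Chennai is entirely South Indian, the country effect adjusted for origin rests essentially on the same stratum.
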